ZIIP Acne Protocol October 5, 2020

Evaluation of the Safety and Efficacy of an Acne Treatment Device

| STUDY NUMBER | DCS-46-20 |
|----------------------------|--|
| INVESTIGATOR | [name] |
| STUDY SITE | Dermatology Consulting Services, PLLC [name] T [contact] F [contact] [contact] |
| INSTITUTIONAL REVIEW BOARD | Allendale Institutional Review Board (AIRB) [name] T [contact] F [contact] |
| SPONSOR | ZIIP Inc. |
| INVESTIGATIONAL DEVICE | ZIIP Device |
| SPONSOR PRIMARY CONTACT | [name] |
| STUDY DESIGN | Monadic device, historical control |
| VERSION NUMBER | 6 |

This document is confidential and contains proprietary information of Dermatology Consulting Services, PLLC. Neither this document nor any information contained herein can be reproduced or disclosed to others without written consent of Dermatology Consulting Services, PLLC.

| Dermatology Consulting Services, PLLC | PAGE 2 of 2 |
|--|-------------|
| PROTOCOL NUMBER: DCS-46-20 | |
| STUDY TITLE: Evaluation of the Safety and Efficacy of an Acne Treatmen | nt Device |
| PROTOCOL SYNOPSIS AND BUDGET DATE: August 1, 2020 | |
| PROTOCOL DATE: October 5, 2020 | |
| ANTICIPATED STUDY RUN DATES: TBD | |
| ANTICIPATED FINAL REPORT DATE: TBD | |
| This document represents the final approved protocol ready for IRB su | bmission. |
| Representative Date ZIIP | |

Date

[name].
Primary Investigator
Dermatology Consulting Services, PLLC

[name]

STUDY NUMBER 1

- 1. Error! Bookmark not defined.
- 2. Error! Bookmark not defined.
- 3. Error! Bookmark not defined.
- 4. Error! Bookmark not defined.
- 5. Error! Bookmark not defined.
- 6. Error! Bookmark not defined.
 - 6.1 Error! Bookmark not defined.
 - 6.2 13
 - 6.3 Error! Bookmark not defined.
 - 6.4 Error! Bookmark not defined.
 - 6.5 Error! Bookmark not defined.
- 7. Error! Bookmark not defined.
 - 7.1 15
 - 7.1.1 Error! Bookmark not defined.
 - 7.1.2 Error! Bookmark not defined.
 - 7.1.3 Error! Bookmark not defined.
 - 7.1.4 15
 - 7.1.5
 - 7.1.6 15
 - 7.2 15
 - 7.2.1 16
 - 7.2.2 16
 - 7.2.3 17
 - 7.2.4 17
 - 7.2.5 18
- 8. Error! Bookmark not defined.
 - 8.1 Error! Bookmark not defined.
- 9. Error! Bookmark not defined.
 - 9.1 Error! Bookmark not defined.
- 10. Error! Bookmark not defined.
 - 10.1 Error! Bookmark not defined.
 - 10.2 Error! Bookmark not defined.
 - 10.3 Error! Bookmark not defined.
 - 10.4 Error! Bookmark not defined.
 - 10.5 Error! Bookmark not defined.

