6.3 INCLUSION CRITERIA

The following items represent the inclusion criteria:

- 1. Subjects with mild to moderate acne (5-30 inflammatory lesions and no nodules/cysts).
- 2. Male and female subjects age 18-50 years.
- 3. Subjects with all Fitzpatrick skin types.
- 4. Subjects of all complexion types (normal, oily, dry, combination).
- 5. Subjects who have used the same moisturizer without difficulty for 30 days and will continue using same moisturizer during the 12 week study.
- 6. Subjects agree not to introduce any new colored cosmetics (lipsticks, eye shadows, facial foundations, blush, & powder).
- 7. Subjects who are using no other acne products for the duration of the study.
- 8. No known medical conditions that, in the investigator's opinion, may interfere with study participation.
- 9. Women of childbearing potential must be willing to use a form of birth control during the study. For the purpose of this study, the following are considered acceptable methods of birth control: oral contraceptives, Norplant®, Depo-Provera®, double barrier methods (e.g., condom and spermicide) and abstinence.
- 10. Subjects have signed an Informed Consent Form in compliance with 21CFR, Part 50: "Protection of Human Subjects."
- 11. Subjects are dependable and able to follow directions and willing to comply with the schedule of visits.

12. Subjects in generally good physical and mental health.

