6.4 EXCLUSION CRITERIA

The following items represent the exclusion criteria:

- 1. Any dermatological disorder, which in the investigator's opinion, may interfere with the accurate evaluation of the subject's skin characteristics, except for the study condition of acne.
- 2. Subjects who are not willing to use the assigned study device to their face as instructed.
- 3. Subjects who have used any topical prescription or OTC acne products for 2 weeks prior to study entry.
- 4. Subjects who have taken any oral prescription or OTC acne products for 4 weeks prior to study entry.
- 5. Subjects who have used a non-OTC cleanser without benzoyl peroxide, sulfur or salicylic acid for at least 2 weeks prior to study entry.
- 6. Subject who have not had any facial treatments in the past 6 months and are willing to withhold all facial treatments during the course of the study including facials, facial peels, photo facials, laser treatments, dermabrasion, botulinum toxin (Botox), injectable filler treatments, intense pulsed light (IPL), acid treatments, tightening treatments, and/or facial plastic surgery.
- 7. Subjects who are pregnant, breast feeding or planning a pregnancy.
- 8. Subjects with clinically significant and/or unstable medical disorders.
- 9. Subjects who are unwilling or unable to comply with the requirements of the protocol.
- 10. Subjects who have a history of a psychological illness or condition that would interfere with their ability to understand and follow the requirements of the study.
- 11. Subjects who have undergone recent facial surgery.
- 12. Subjects currently participating in any other clinical trial.
- 13. Subjects having started hormone replacement therapies (HRT) or hormones for birth control less than 3 months prior to the study entry; or who plan on starting, stopping or changing doses of HRT or hormones for birth control during the study.
- 14. Subjects who have a cardiac pacemaker, implanted defibrillator, or other implanted metallic or electronic device.
- 15. Subjects who are wearing EKG monitoring equipment.
- 16. Subjects with phlebitis, thrombophlebitis, broken capillaries, or varicose veins.
- 17. Subjects who have seizures, epilepsy, or cancer/tumors.
- 18. Subjects who have a history of hypertrophic scarring or keloid formation.

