6.5 CONCOMITANT MEDICATIONS

All oral and topical prescription medications should remain unchanged during the study. No oral or topical over the counter or prescription acne medications are allowed. No other acne products other than the study products are allowed during the study.

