7.1.2 MEDICAL HISTORY

An abbreviated medical history including current medications shall be recorded.

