10.5 STORAGE AND ACCOUNTABILITY OF STUDY PRODUCT

The study product will be stored at room temperature, away from sunlight, in a locked, limited access area at the study site. Access to the study product will be limited to the investigator and staff members designated to dispense study medication. A study product log will be used to record the dispensation and return of all study products. The subject number/initials, and the initials and date of the person dispensing and receiving the returned study product will be documented on this form.

10.6

CODE DISCLOSURE

The study coordinator will not develop a code as all subjects will use the active device and electroconductive media in this monadic study.

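### Exclusion 13 looks back before entry only for hormones that were started, so a subject who stopped or changed dose just before baseline is eligible, and any resulting acne change cannot be separated from the device effect

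*Combined protocol and SAP*

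**What the plan says.** Item 13 of section 6.4 has two parts. The part that looks back from entry excludes "Subjects having started hormone replacement therapies (HRT) or hormones for birth control less than 3 months prior to the study entry". The part that looks forward excludes those "or who plan on starting, stopping or changing doses of HRT or hormones for birth control during the study". The synopsis carries the same criterion.

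Other provisions that bear on it:

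- Section 6.5 asks for stable prescriptions, but only from entry onwards: "All oral and topical prescription medications should remain unchanged during the study".
- Exclusion 4 has a 4-week look-back limited to acne products: "Subjects who have taken any oral prescription or OTC acne products for 4 weeks prior to study entry".
- Inclusion 9 (section 6.3) accepts these contraceptive methods: "oral contraceptives, Norplant®, Depo-Provera®, double barrier methods (e.g., condom and spermicide) and abstinence". Current hormone users and recent former users can both qualify.
- Section 7.1.2 limits the history taken at enrollment: "An abbreviated medical history including current medications shall be recorded".

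On design, the title page says "Monadic device, historical control", and section 10.6 says that "all subjects will use the active device and electroconductive media in this monadic study". Section 12.5 defines efficacy as improvement in IGA at 12 weeks relative to baseline. Section 12 tests ordinal data with the Wilcoxon signed rank test and specifies neither a comparison with a historical control nor an adjustment for hormone use.

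**The concern.** During the study, the plan treats three hormonal events as reasons to keep a subject out: starting, stopping and changing dose. Before entry it screens for only the first, and it gives no reason for the difference. A woman who stopped an oral contraceptive the week before baseline, and now uses a double barrier method or abstinence, passes item 13 and inclusion 9.

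In a randomized trial such subjects would be expected to fall evenly between arms. Here there is no concurrent arm, and the subject's own baseline is the only comparator the analysis uses. If her acne moves over the 12 weeks because of the hormonal change, that movement goes straight into the efficacy estimate. An improvement would be credited to the device; a worsening would hide a real effect. Because the history need only name current medications, a hormone already stopped may leave no trace in the data, and a later sensitivity analysis could not find these subjects.

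**Working it through.** **Step 1. The two parts of item 13 side by side.**

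| Hormonal event | Before entry | During the study |
|---|---|---|
| Starting | Excluded if less than 3 months before | Excluded if planned |
| Stopping | Not mentioned | Excluded if planned |
| Changing dose | Not mentioned | Excluded if planned |

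**Step 2. Does anything else close the two empty cells?**

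- *Section 6.5*: applies during the study only.
- *Exclusion 4*: reaches a hormone only if it was taken as an oral acne product, and only for 4 weeks.
- *Exclusion 7*: reaches a woman who stopped in order to conceive, because she is planning a pregnancy. It does not reach other reasons for stopping.
- *Inclusion 8 and exclusion 8*: concern medical conditions and disorders and leave room for judgement. They do not mention hormone changes.
- *Section 7.1.2 and the medication review in section 2*: they record, but do not exclude. A stopped hormone is not a current medication. A hormone still taken at a new dose would be listed, but no date of change is requested.

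So the gap is narrowed in places but not closed.

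**Step 3. How much could it matter?** The plan has no figure to reproduce: section 12.1 says only that the sponsor chose 50 subjects, with no effect size, SD or power. The following is illustration.

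Inputs from the plan: n = 50; two-sided 0.05 (section 12.2), so 2.5% in each direction and a critical value of 1.96. Assumptions: no device effect; a share *f* of subjects affected; each shifted by *s* SDs of the IGA change, all in the same direction.

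- Bias in the mean change = *f* × *s*
- SD of the change = √(1 + *f*(1 − *f*)*s*²)
- P(significant in the direction of the shift) = Φ(*f s* √50 / SD − 1.96)

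Worked case, *f* = 0.02 (one subject in 50), *s* = 1: bias 0.02; SD = √(1 + 0.02 × 0.98) = 1.0098; 0.02 × 7.071 / 1.0098 = 0.140; Φ(0.140 − 1.96) = 3.4%.

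Two in 50, *f* = 0.04, *s* = 1: bias 0.04; SD = √(1 + 0.04 × 0.96) = 1.019; 0.04 × 7.071 / 1.019 = 0.278; Φ(0.278 − 1.96) = 4.6%.

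| Share affected (expected number of 50) | *s* = 0.5 SD | *s* = 1 SD |
|---|---|---|
| 0% (0) | 2.5% | 2.5% |
| 2% (1) | 2.9% | 3.4% |
| 4% (2) | 3.4% | 4.6% |
| 5% (2.5) | 3.7% | 5.3% |
| 10% (5) | 5.4% | 10.0% |

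For scale, a sample of 50 detects a standardized paired change of (1.96 + 0.84) / √50 = 0.40 with 80% power. The biases for one or two subjects, 0.02 and 0.04 SD at *s* = 1, are a twentieth and a tenth of that.

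**Step 4. Same question with the planned test.** A simulation of the Wilcoxon signed rank test (4,000 runs, n = 50) assumed null IGA changes of −1, 0 and +1 in 20%, 60% and 20% of subjects, and a full one-grade shift in each affected subject. A significant result in the direction of the shift occurred in about 7% to 8% of runs with 5% affected and about 16.5% with 10% affected. These rates are higher than in the table because the assumed shift is larger: the null SD is √0.4 = 0.63 grades, so one grade is 1 / 0.63 = 1.6 SD. The results were nearly symmetric: a shift towards worsening gave about the same rates against the device.

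**The case against.** The strongest case against the point concerns its consequences. No passage says that stopping a hormone or changing its dose leaves an effect on acne, how long it lasts or which way it goes. Three stronger readings are tempting, and the documents support none of them.

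- *That the gap biases the result in favour of the device.* The direction is not given; masking is as possible as inflation.
- *That the plan's own 3-month window, being longer than 12 weeks, shows a change made just before entry acts throughout follow-up.* The window is stated for starting only and carries no rationale. It cannot be read as a duration of effect for stopping or dose changes.
- *That each affected subject moves the proportion improved by 2 percentage points (1/50), so that two to five subjects move it by 4 to 10.* The plan defines no responder endpoint. The figure also needs every affected subject to change category, all the same way, so it is an upper bound on a quantity that the plan does not analyse. The count of two to five has no source.

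It is also fair to say that exclusions 4 and 7 catch some cases, and that a switch to a new preparation might be read as starting. The absence of a concurrent control is the larger weakness; closing this gap would not make the baseline comparison interpretable by itself.

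All of that limits the size of the point. It does not remove the inconsistency: the plan bars stopping and dose changes during the study, does not screen for them before it, and need not record them.

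**Conclusion.** The point holds as a gap in one eligibility criterion, present in both section 6.4 and the synopsis. Subjects who stopped or changed dose of HRT or birth-control hormones shortly before baseline are eligible, and any acne change that follows, in either direction, is inseparable from the device effect in this single-arm comparison with baseline.

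Its size is unknown from the documents. Under the assumptions above, it is small if one or two of 50 subjects are affected (3.4% to 4.6% against a nominal 2.5%, for a 1 SD shift). It becomes material only with about five affected and a consistent shift of 1 SD or more (10% in the approximation, about 16.5% in the one-grade simulation). Those larger figures rest on shares and shifts that the plan neither gives nor implies, so they should not be quoted as expected bias. The case for acting is that the correction is cheap and removes a source of disturbance that the plan itself guards against once the study has begun.

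**What to change.** 1. In section 6.4 item 13 and in the synopsis, reconcile the two parts so that the pre-entry look-back also names stopping and dose changes. The existing 3-month window is the natural default for consistency; its length for these two events is a clinical matter for the sponsor to confirm.
2. In section 7.1.2, widen the baseline medication history beyond current medications: record the date and type (start, stop or dose change) of the last hormonal change. That makes the criterion checkable and allows a sensitivity analysis if a subject is enrolled in error.

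The cost is a few words in two places, one question at a visit where medications are already reviewed, and a few women deferred or excluded. The sample size and the planned tests do not change.

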6.5 CONCOMITANT MEDICATIONS

All oral and topical prescription medications should remain unchanged during the study. No oral or topical over the counter or prescription acne medications are allowed. No other acne products other than the study products are allowed during the study.

7. CONDUCT OF STUDY: METHODS AND PROCEDURES

7.1 ENROLLMENT

7.1.1 INFORMED CONSENT

A signed informed consent form shall be obtained from each subject prior to study enrollment and performing any study procedures. No study related procedures or activities shall be performed until each subject is fully informed and the consent form is signed and dated.

7.1.2 MEDICAL HISTORY

An abbreviated medical history including current medications shall be recorded.

7.1.3 DERMATOLOGICAL EXAMINATION

A dermatological examination shall be performed to insure subjects possess acne and meet all inclusion criteria and none of the exclusion criteria.

7.1.4 STUDY PROCEDURES

The subjects will be screened for the inclusion and exclusion criteria prior to study enrollment. Only subjects who meet all the requirements, have signed an informed consent, and have given a medical history shall be entered into the study. All other subjects shall be considered screening failures.

7.1.5 STUDY MATERIAL ADMINISTRATION

All subjects will use the active ZIIP device as currently marketed. The ZIIP Device will be customized for the delivery of acne treatment with -400 microamps direct current, applied 3 days per week on non-consecutive days, on each facial zone afflicted by acne. A electroconductive media will be applied to each facial zone afflicted by acne prior to initiation of the device treatment.

7.1.6 SCREENING PROCEDURES

Potential volunteers will be enrolled based on the presence of mild to moderate acne and their ability to meet the inclusion/exclusion criteria required for study enrollment.

7.2 STUDY CONDUCT PROCEDURES

7.2.1 BASELINE

Male and female subjects will be enrolled in this single-site monadic study to evaluate the effect of a direct current device on acne treatment. Subjects who sign the informed consent form and meet all inclusion criteria and none of the exclusion criteria will be enrolled at the baseline visit. Subjects will be asked to continue their self-selected moisturizer, nonmedicated cleanser, and sunscreen they have used without difficulty for the prior 30 days and for the 12 week study. Subjects must also continue all facial products and cosmetics unchanged for the duration of the study. No other oral or topical acne products can be used. Subjects must be washed out of all topical acne products for at least 2 weeks and all oral acne products for at least 4 weeks. Subjects must possess mild to moderate acne with 5-30 inflammatory lesions and no nodules/cysts.

At baseline visit, the dermatologist investigator will assess the face for the investigator global acne assessment (IGA) based on the following 5 point ordinal scale: 0=clear, 1=almost clear, 2=mild, 3=moderate, and 4=severe. In addition, the dermatologist investigator will perform an inflammatory and noninflammatory lesion count within each facial quadrant (zone). The subjects will then be provided the study device and electroconductive media for every other day use after cleansing to the acne afflicted facial zones. The first use of the device will occur at the research center to ensure all subjects are using the device properly.

The dermatologist investigator will assess the tolerability of the device in terms of peeling, dryness, redness, and swelling on a 5-point ordinal scale (0=none, 1=minimal, 2=mild, 3=moderate, and 4=severe). The subjects will then assess device tolerability in terms of itching, burning, redness, and swelling. All assessments will be made on a 5-point ordinal scale (0=none, 1=minimal, 2=mild, 3=moderate, and 4=severe). Subjects will be given their diaries and asked to return to the research center in 2 weeks. A reminder text will be sent to encourage compliance prior to the week 2 visit.

All investigator selected subjects will be photographed with the Canfield VISIA CR using Standard 1 lighting at baseline, week 2, week 4, and week 8, and week 12.

7.2.2 WEEK 2

At the week 2 visit, the dermatologist investigator will assess the face for the investigator global acne assessment (IGA) based on the following 5 point ordinal scale: 0=clear, 1=almost clear, 2=mild, 3=moderate, and 4=severe. In addition, the dermatologist investigator will perform an inflammatory and noninflammatory lesion count within each facial quadrant. The study device

will be inspected for proper operation and the study diary will be inspected for compliance.

The dermatologist investigator will assess the tolerability of the device in terms of peeling, dryness, redness, and swelling on a 5-point ordinal scale (0=none, 1=minimal, 2=mild, 3=moderate, and 4=severe). The subjects will then assess device tolerability in terms of itching, burning, redness, and swelling. All assessments will be made on a 5-point ordinal scale (0=none, 1=minimal, 2=mild, 3=moderate, and 4=severe). The subjects will also complete a sponsor provided marketing questionnaire. Subjects will be asked to return to the research center at week 4. A reminder text will be sent to encourage compliance prior to the week 4 visit.

All investigator selected subjects will be photographed with the Canfield VISIA CR using Standard 1 lighting at baseline, week 2, week 4, and week 8, and week 12.

7.2.3 WEEK 4

At the week 4 visit, the dermatologist investigator will assess the face for the investigator global acne assessment (IGA) based on the following 5 point ordinal scale: 0=clear, 1=almost clear, 2=mild, 3=moderate, and 4=severe. In addition, the dermatologist investigator will perform an inflammatory and noninflammatory lesion count within each facial quadrant. The study device will be inspected for proper operation and the study diary will be inspected for compliance.

The dermatologist investigator will assess the tolerability of the device in terms of peeling, dryness, redness, and swelling on a 5-point ordinal scale (0=none, 1=minimal, 2=mild, 3=moderate, and 4=severe). The subjects will then assess device tolerability in terms of itching, burning, redness, and swelling. All assessments will be made on a 5-point ordinal scale (0=none, 1=minimal, 2=mild, 3=moderate, and 4=severe). The subjects will also complete a sponsor provided marketing questionnaire. Subjects will be asked to return to the research center at week 8. A reminder text will be sent to encourage compliance prior to the week 8 visit.

All investigator selected subjects will be photographed with the Canfield VISIA CR using Standard 1 lighting at baseline, week 2, week 4, and week 8, and week 12.

7.2.4 WEEK 8

At the week 8 visit, the dermatologist investigator will assess the face for the investigator global acne assessment (IGA) based on the following 5 point ordinal scale: 0=clear, 1=almost clear, 2=mild, 3=moderate, and 4=severe. In addition, the dermatologist investigator will perform an inflammatory and

noninflammatory lesion count within each facial quadrant. The study device will be inspected for proper operation and the study diary will be inspected for compliance.

The dermatologist investigator will assess the tolerability of the device in terms of peeling, dryness, redness, and swelling on a 5-point ordinal scale (0=none, 1=minimal, 2=mild, 3=moderate, and 4=severe). The subjects will then assess device tolerability in terms of itching, burning, redness, and swelling. All assessments will be made on a 5-point ordinal scale (0=none, 1=minimal, 2=mild, 3=moderate, and 4=severe). The subjects will also complete a sponsor provided marketing questionnaire. Subjects will be asked to return to the research center at week 12. A reminder text will be sent to encourage compliance prior to the week 12 visit.

All investigator selected subjects will be photographed with the Canfield VISIA CR using Standard 1 lighting at baseline, week 2, week 4, and week 8, and week 12.

7.2.5 WEEK 12

At the week 12 visit, the dermatologist investigator will assess the face for the investigator global acne assessment (IGA) based on the following 5 point ordinal scale: 0=clear, 1=almost clear, 2=mild, 3=moderate, and 4=severe. In addition, the dermatologist investigator will perform an inflammatory and noninflammatory lesion count within each facial quadrant. The study device will be inspected for proper operation and the study diary will be inspected for compliance. The diary and the study materials will be collected.

The dermatologist investigator will assess the tolerability of the device in terms of peeling, dryness, redness, and swelling on a 5-point ordinal scale (0=none, 1=minimal, 2=mild, 3=moderate, and 4=severe). The subjects will then assess device tolerability in terms of itching, burning, redness, and swelling. All assessments will be made on a 5-point ordinal scale (0=none, 1=minimal, 2=mild, 3=moderate, and 4=severe). The subjects will also complete a sponsor provided marketing questionnaire. Subjects will complete their study participation at this time.

All investigator selected subjects will be photographed with the Canfield VISIA CR using Standard 1 lighting at baseline, week 2, week 4, and week 8, and week 12.

